4.1 Primary Objective(s)

4.1.1 Primary Efficacy Objective

Demonstrate the superiority of the MARVEL 2 features to provide atrioventricular synchronous pacing relative to Micra VVI pacing in subjects with normal sinus node function and persistent 3rd degree AV block at rest.

4.1.2 Primary Safety Objective

Demonstrate that the MARVEL 2 features provide pacing as intended.

4.2 Secondary Objective

Demonstrate an increase in stroke volume, as measured by left ventricular outflow tract velocity time integral, with the MARVEL 2 features compared to VVI pacing in subjects with normal sinus node function and persistent 3rd degree AV block.

[Redacted content]

5. Investigation Plan

5.1 Study Design

The MARVEL 2 study is an acute, prospective, global, multi-center, software-download clinical study to evaluate the performance of the MARVEL 2 software, which includes a comprehensive set of the anticipated Micra AV features. The study is planned to be conducted in the US, Europe and Asia. In the United States, the study is being conducted under an Investigational Device Exemption (IDE). Overall, the study is expected to be conducted at approximately 15-20 centers and will enroll up to 100 subjects to obtain at least 70 usable Holter datasets to meet the sample size required to test the primary objectives of the study. Holter datasets will be considered usable if there is readable telemetry signal as determined by Medtronic personnel experienced in the review of Holter recordings.

[figure not shown]
The expected total study duration (from first subject enrollment to the exit of the last subject) is approximately 6-months. This represents the time necessary to enroll the target sample size of at least 70 subjects. A download study into patients with an existing Micra device allows the new algorithm performance to be measured in patients where a Micra device has already been chosen as most appropriate for the patient. Most enrolled subjects will complete the study procedures at a single 2 to 4-hour study visit. However, a subset of subjects who enroll in the study at the time of their Micra implant (anticipated to be approximately 10 subjects) will have the investigational algorithm downloaded following Micra implant, one day post-implant, and at approximately 1-month post-implant. Studying these subjects with *de novo* Micra implants will allow the MARVEL 2 software features to be tested at multiple points in the device life cycle.

Additionally, study centers that participated in the MARVEL study may enroll up to three randomly selected subjects with normal sinus node function and persistent 3rd degree AV node block that participated in the MARVEL study. Allowing subjects enrolled in the MARVEL study to participate in the MARVEL 2 study will enable an assessment of AV synchrony at multiple points in time.

Because the download algorithm running in Micra device significantly increases current drain, a 2 to 4-hour acute study is used to limit the reduction in device longevity.

Figure 1 displays the MARVEL 2 study flow for all study subjects.

Figure 1: MARVEL 2 Study Flow

[figure not shown]
5.1.1 De novo subjects

De Novo subjects are those subjects that enroll in the MARVEL 2 study at the time of their Micra implant. Note that these will be subjects where the clinician and patient have determined that a Micra device is the most appropriate therapy for the patient's condition. It is expected that approximately 10 *de novo* subjects will enroll in the MARVEL 2 study. Studying these subjects with *de novo* Micra implants ensures some accelerometer signals are collected during or immediately after the implant procedure. In addition, studying these subjects prior to hospital discharge and at 1-month provides information on the evolution of the accelerometer signal and AV synchrony.

Specifically, following Micra implant and initial device interrogation, the investigational MARVEL 2 software will be downloaded into the Micra and a custom Holter monitor will be placed on the subject. The Holter monitor will record surface ECG, EGM, accelerometer signals, and device and MARVEL 2

algorithm markers. The subject should be in a sitting or supine position while the automatic setup runs for approximately 20 minutes. Once completed, the MARVEL 2 software will be removed from the Micra and Holter monitor removed from the subjects. Note that the MARVEL 2 software will be in monitor mode (VDI mode with no atrial tracking) on the day of the Micra implant. Prior to hospital discharge and at approximately 1-month post-implant *de novo* subjects will perform the MARVEL 2 study procedures as described in Figure 2.

Figure 2: Additional Study Procedures for De Novo Subjects

5.1.2 Reenrollment of MARVEL study subjects

Study centers that participated in the MARVEL study can reenroll up to 3 subjects in the MARVEL 2 study from their subjects who had normal sinus node function and persistent 3rd degree AV block during Holter monitoring in the MARVEL study. To avoid selection bias when considering reenrollment, centers

that had 3 or fewer eligible subjects are required to approach all their eligible subjects for reenrollment while centers with more than 3 eligible subjects will be given a randomly permuted list of subjects to approach for reenrollment in MARVEL 2 (note that these centers are required to approach the subjects in order of their permuted list until up to 3 subjects are reenrolled). Based on this strategy, a maximum of 24 reenrollments may occur if all MARVEL centers participate in MARVEL 2 and all eligible MARVEL subjects enroll in the MARVEL 2 study (note, not all centers had 3 eligible subjects).

5.2 Study Population

The target population will consist of patients ≥ 18 years in age, with documented history of AV block, and implanted with a Micra with remaining device longevity of 6 years or more or expected to be implanted with a Micra.

5.3 Study Procedures

Study procedures for subjects with existing Micra devices will be conducted in a one day in-office visit. Study procedures for *de novo* subjects with a new Micra implant will be conducted over a 1-month period to collect the study procedures at up to 3 points in time. Data collection specific for the MARVEL 2 study are summarized in Table 1.

Table 1: Summary of Study Procedures

MARVEL 2 Study Data Collection	Micra In-clinic Subject		Micra De Novo Subject			
	Baseline	MARVEL 2 Procedure	Baseline	Implant	Pre-Hospital Discharge MARVEL 2 Procedure	1 month-MARVEL 2 Procedure
Inclusion/exclusion assessment	X		X			
Patient informed consent	X		X			
Demographics and pacing indication	X		X			
Medical history	X		X		X	X
Micra Implant				X		
Cardiovascular medications	X		X		X	X
Physical Examination	X		X		X	X
12 Lead ECG	X		X		X	X
X-Ray image(s) of Micra implant location	X ¹		X ¹			
Initial device interrogation Save to media		X		X	X	X
Download MARVEL 2 software		X		X	X	X
Holter monitoring (Auto Set-up phase) VDI data collection Selects best vector combination Selects sensing parameters		X		X	X	X
Holter monitoring (In-clinic Evaluation phase) Perform quiet resting period Perform posture testing and hall walks Accelerometer Characterization		X			X	X
Echocardiogram		X			X	X
Remove MARVEL 2 software		X		X	X	X
Final device interrogation Save to media		X		X	X	X
Study exit		X				X
Adverse Events	If Occur					
Study Deviations						
Device Deficiencies						
System Modification						

¹If available. If not available, no additional x-ray images will be collected.

6. Determination of Sample Size

A sample size of at least 70 subjects with usable Holter datasets, of which at least 35 have a predominant rhythm of persistent 3rd degree AV block with normal sinus function, is required to test the study's primary objectives. For details of the sample size calculation see Sections 7.5.3.5, 7.5.4.5, and 7.5.5.5.

7. Statistical Methods

7.1 General Considerations

7.1.1 Report for which this Statistical Analysis Plan Applies

[REDACTED] This SAP applies to the final study report and to any publication(s) reporting the results of the MARVEL 2 primary and secondary objectives.

7.1.2 Analysis Timing

There will be one formal analysis of the study's primary, secondary, [REDACTED] objectives, which will occur once all enrolled subjects have had the opportunity to complete the study and the study databases have been locked.

7.1.3 Type I Error Control

For the study to be considered a success, the null hypothesis for both the primary efficacy and safety objectives must be rejected. Additionally, to make a statistically valid claim of significance for the secondary objective, the null hypothesis for both primary objectives must be rejected and the null hypothesis for the secondary objective must be rejected. This testing strategy guarantees a study wide type I error rate of 0.05.

7.1.4 Usable Holter Datasets

A Holter dataset (i.e. device data telemetered to the Holter flash memory and surface ECG recordings) will be considered usable if there is readable telemetry signal as determined by the presence of visible device and algorithm marker channel. Additionally, to be included in the analysis of study objectives that require assessment of AV synchrony (i.e. primary efficacy objective, [REDACTED]

[REDACTED] visible P-waves must be present on the ECG recordings.

7.1.5 Determination of Predominant Heart Rhythm

Holter data from the approximately 20-minute auto-setup phase will be used to determine each subject's predominant heart rhythm during the Holter monitoring session. The sinus node function will be categorized as normal sinus, sinus node dysfunction (sinus bradycardia, sinus tachycardia, other) or atrial arrhythmia. The AV conduction status will be categorized as persistent 3rd degree AV block or

intact AV conduction. Note that subjects with a predominant rhythm of persistent 3rd degree AV block with normal sinus function will be included in the analysis of the primary efficacy objective.

[Redacted]

[Redacted]

[Redacted]

7.2 General Summaries

7.2.1 Baseline and Medical History

Standard baseline and relevant medical history will be collected on the e-CRFs for all enrolled subjects. Baseline and medical history variables to be summarized include, but are not limited to: age, sex, cardiovascular history, arrhythmia history, and cardiovascular medications.

For continuous variables, mean, standard deviation, median, and range will be reported. For categorical variables, frequency and percentage will be reported. Baseline information will be summarized for all enrolled subjects and for subjects with usable Holter data. Additionally, baseline and medical history will be summarized for the following subsets of subjects:

1. Subjects included in the analysis of the primary efficacy objective (i.e. those with a predominant rhythm during Holter monitoring of persistent 3rd degree AV block)

7.2.2 Clinical Investigation Plan (CIP) Deviations

Deviations from the clinical investigation plan will be collected as deviations on the Study Deviation e-CRF as they occur. Deviations will be summarized in a table by category. The number of deviations per category, and the number and percentage of subjects with a deviation in each category will be reported.

7.2.3 Adverse Events

All adverse events regardless of severity or relationship to the MARVEL 2 algorithm will be collected during the study on the Adverse Event e-CRF as they occur. Section 7.5.6.7 describes the methods that will be used to summarize adverse events.

7.2.4 Subject Disposition

The number of enrolled subjects and number of subjects with usable Holter data will be reported by study center and country.

The number and percentage of enrolled subjects exiting the study will be summarized by subject status term on the Study Exit e-CRF. As the majority of subjects will complete the study procedures during a single study visit, premature study exit is not expected.

A narrative of any subject deaths occurring during the study period will be provided in the final study report.

7.3 Center Pooling

The study is expected to be conducted in approximately 15-20 centers in Europe, USA and Asia. Study results are not expected to differ by study center, therefore data from all centers will be pooled. There will be no minimum limit that each investigator must enroll. The maximum number of enrolled subjects per center is 20 subjects.

[figure not shown]
7.4 Interim Analyses

No interim analysis of the study objectives is planned for this study.

7.5 Evaluation of Objectives

7.5.1 Holter Data Preprocessing

Following download of the investigational MARVEL 2 software, a Holter monitor will be placed on the subjects for the duration of study procedures. The Holter monitor continuously records surface ECG, EGM, accelerometer signals, and device and MARVEL 2 algorithm markers are telemetered from the implanted Micra device. The marker channel includes the ventricular sensed and paced event markers as well as markers unique to the MARVEL 2 features including whether the MARVEL 2 features sense an atrial beat (A4 signal). In addition, the Holter records supplemental marker data from the Micra including V-V interval, pacing mode, pacing amplitude, and MARVEL 2 specific settings and measurements, including A4 amplitude and mode switch status.

[Redacted]

[Redacted]

Each Holter dataset will be reviewed by Medtronic personnel experienced in the review of Holter recordings to determine the recording time, quality of the recording, and confirm correct MARVEL 2 feature operation.

[Redacted]

[REDACTED]

7.5.2 Initial Processing

[REDACTED]

[REDACTED]

[REDACTED]

[REDACTED]

[REDACTED]

[Redacted text block]

[Redacted text block]

[Redacted text block]

[Redacted text block]

[Redacted text block]

[Redacted text block]

[Redacted text block]

[Redacted text block]

[Redacted text block]

[Redacted text block]

[Redacted text block]

[Redacted text block]

[Redacted text block]

[Redacted text block]

[Redacted text block]

[Redacted text block]

[Redacted text block]

[Redacted text block]

[Redacted text block]

[Redacted text block]

[Redacted text block]

[Redacted text block]

[Redacted text block]

[Redacted text block]

[Redacted text block]

[Redacted text block]

[Redacted text block]

[Redacted text block]

[Redacted text block]

[Redacted text block]

[Redacted text block]

[Redacted text block]

[Redacted text block]

[Redacted text block]

[Redacted text block]

[Redacted text block]

[Large redacted text block]

[Redacted text block]

[Redacted text block]

[Redacted text block]

[Redacted text line]

[Redacted text line]

[Redacted text line]

[Redacted text line]

[Redacted text line]

[Redacted text line]

[Redacted text line]

[Redacted text line]

[Redacted text line]

[Redacted text line]

[Redacted text line]

[Redacted text line]

[Redacted text line]

[Redacted text line]

[Redacted text line]

[Redacted text line]

[Redacted text line]

[Redacted text line]

[Redacted text line]

[Redacted text line]

[Redacted text line]

[Redacted text line]

[Redacted text line]

[Redacted text line]

7.5.3 Primary Efficacy Objective

Demonstrate the superiority of the MARVEL 2 features to provide atrioventricular synchronous pacing relative to Micra VVI pacing in subjects with normal sinus node function and persistent 3rd degree AV block.

7.5.3.1 Endpoint Definition

A subject will meet the primary efficacy endpoint if a paced or sensed ventricular beat is within 300 ms following an ECG confirmed P-wave for at least 70% of the ECG confirmed P-waves. The primary endpoint will be evaluated during the MARVEL 2 setup phase (VDI pacing which is effectively VVI pacing) and during the resting period in which the MARVEL 2 features are enabled.

Rationale for the endpoint is provided in section 8.2.1.1 of version 2 of the MARVEL CIP.

7.5.3.2 Hypothesis

$H_0: \pi_{AV} = \pi_{VVI}$, versus

$H_a: \pi_{AV} \neq \pi_{VVI}$

where π_{AV} is the proportion of subjects meeting the primary efficacy endpoint during MARVEL 2 adaptive mode (VDD) pacing, and π_{VVI} is the proportion of subjects meeting the primary efficacy endpoint in VVI mode.

7.5.3.3 Performance Requirements

The percentage of subjects meeting the primary endpoint in the MARVEL 2 adaptive pacing mode is significantly greater (at the 0.05 level) than the percentage of subjects meeting the endpoint in VVI pacing mode.

Meeting the performance requirement for the primary efficacy objective will demonstrate that the MARVEL 2 features provide high rates of atrioventricular synchronous pacing and greatly exceed rates

observed with VVI pacing in the patient population expected to benefit the most from atrioventricular synchronous pacing.

7.5.3.4 Analysis Methods

For each subject, the VVI pacing control period will occur shortly following investigational software download during the approximately 20-minute algorithm auto-setup phase where the MARVEL 2 programmable parameters are setup to enable optimal tracking of the A4 signal. The auto-setup phase will occur while the MARVEL 2 features are in monitor mode (i.e. VDI pacing which is effectively VVI pacing). For purposes of evaluating the primary efficacy objective, the 20-minute resting period while the MARVEL 2 features are programmed to adaptive mode and providing VDD pacing will serve as each subject's treatment period.

Note that a randomized crossover design will *not* be used to compare AV synchronous pacing percentage between the MARVEL 2 pacing mode and VVI pacing for the following reasons: 1) knowledge of pacing mode is unlikely to influence AV synchronous pacing rate as such knowledge is unlikely to influence right atrial contractility, 2) the auto-setup phase will provide an opportunity to assess the AV synchronous pacing percentage during VVI pacing, 3) carryover effects are not possible since as soon as the MARVEL 2 features are programmed to adaptive mode atrial tracking will commence.

The accuracy spreadsheet derived from each Holter file (see section 7.5.2.3) will be used to determine the synchrony status (yes or no) for each P-wave. Each accuracy spreadsheet will be imported into SAS and/or R and the P-P interval computed for each P wave i (where $i > 1$) as the time in seconds in Column 1 (A) for the i^{th} P-wave minus the time in seconds in Column 1 (A) for the $i^{\text{th}}-1$ P-wave. Each P-wave in the accuracy spreadsheet file will be classified as being evaluable or not evaluable. P-waves that are not evaluable include:

1. P-waves with no ventricular sense or pace markers and indication of telemetry dropout in the first 300 ms after the P-wave. These are identified from the accuracy spreadsheet where column 13 (M) = 0 and column 14 (N) = 1.
2. P-waves that occur during an AV conduction mode switch as these P-waves occur when the pacing mode is set temporarily to VDI40 while the device checks for intrinsic AV conduction. These are identified from the accuracy spreadsheet where a supplemental marker in the preceding P-P interval (column 15 (O) < P-P interval), and the pacing mode in the supplemental marker is VDI40, indicating a mode switch (column 17 (Q) = 7). Note that for the pacing mode, the supplemental marker indicates the pacing mode on the next ventricular event, which is why a look-back to the preceding supplemental marker is necessary to determine if the current ventricular event is in a mode-switched state.

All other P-waves in the accuracy spreadsheet will be considered evaluable. Evaluable P-waves will be considered synchronous if they occur within 300 ms of the following ventricular event. Thus, evaluable P-waves will be considered synchronous if column 2 (B) < 0.3 and asynchronous if column 2 (B) \geq 0.3.

For the analysis of the primary efficacy objective, P-waves with records in the accuracy spreadsheet corresponding to the auto setup phase (i.e. columns 11 (K) and 12 (L) indicate auto setup phase) or

resting phase (i.e. columns 11 (K) and 12 (L) indicate auto setup phase) will be selected. The auto setup phase will occur during MARVEL 2 monitor mode pacing (i.e. VVI pacing) and the resting phase will occur during MARVEL 2 adaptive mode pacing (i.e. VDD pacing). If at least 70% of evaluable beats are considered synchronous during the VVI or MARVEL 2 adaptive pacing mode during resting, then the subject will be considered to have met the primary efficacy endpoint during the VVI or MARVEL 2 adaptive pacing mode during rest respectively. McNemar's test for paired proportions will be used to test the primary efficacy objective hypothesis. Note that subjects with fewer than 500 evaluable beats during each period will be excluded from the primary efficacy analysis.

[REDACTED]

The following pre-specified subgroups will be evaluated: sex, geography (US versus outside of US), and participation in the MARVEL study (yes versus no). A repeated measures logistic regression model using generalized estimating equations will be used to evaluate the homogeneity of the MARVEL 2 adaptive pacing mode effect on the primary efficacy endpoint by subgroup. For this model, the response will be the primary endpoint status (1=met primary endpoint, 0=did not meet) and the independent variables will be the pacing mode (VVI pacing or MARVEL 2 adaptive mode), subgroup status, and a subgroup status by pacing mode interaction.

[REDACTED]

[REDACTED]

[REDACTED]

Additionally, the proportion of subjects meeting the primary efficacy endpoint will be summarized and compared between VVI pacing and MARVEL 2 adaptive pacing using the methods described above in the following subsets of subjects with normal sinus node function and persistent 3rd degree AV block:

1. Those subjects exhibiting low PVC burden (<5% of cardiac cycles demonstrating evidence of PVC)
2. Those subjects exhibiting low PVC burden with a mitral valve doppler echo E/A ratio of 1.5 or less

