The accelerometer signal is complex and currently is not well understood by clinicians. Therefore, it is desirable to reduce the clinical burden and expertise required to accurately set up the accelerometer detection algorithm. To accomplish this, Medtronic enhanced the MARVEL algorithm to automatically adjust the most often programmed detection parameters. In addition, two mode-switching algorithms were incorporated: (1) a mode-switch to VVI-40 for patients with paroxysmal AV block who often have intact AV conduction and (2) a mode-switch algorithm that switches to VVIR (rate adaptive pacing) if the sensor rate is significantly faster than the VDD rate. The performance of the enhanced algorithm is the focus of the MARVEL 2 study. The MARVEL 2 clinical study will be used as pivotal evidence to support market approval of the Micra AV device for expanding the use of transcatheter pacing systems into patients with AV block and normal sinus node function.

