8.2 Endpoints

8.2.1 Primary Endpoint(s)

8.2.1.1 Primary Efficacy Endpoint

A subject will meet the primary endpoint if a paced or sensed ventricular beat is within 300 ms following an ECG confirmed P-wave for at least 70% of the ECG confirmed P-waves. The primary endpoint will be evaluated during the MARVEL 2 setup phase (VDI pacing which is effectively VVI pacing) and during the 20-minute resting period in which the MARVEL 2 features are enabled.

Rationale for Endpoint

Rationale for 300 ms Synchronous Beat Definition

A paced or sensed R-wave within 300 ms of following an ECG confirmed P-wave that occurs during normal sinus function indicates a level of atrioventricular synchrony that is clinically acceptable. Specifically, currently available dual chamber Medtronic pacing systems utilize the Search AV+[®] algorithm that allows for maximum nominal AV intervals to be lengthened to 290 ms (for intrinsic sensed events) and 320 ms (for paced events) to limit unnecessary ventricular pacing. This feature has been shown to minimize ventricular pacing and reduce atrial fibrillation in patients with sinus node disease.⁷ Therefore, a pace or detection of a sensed R-wave following within 300 ms of an ECG confirmed P-wave would indicate an acceptable level of atrioventricular synchrony.

Additionally, only P-waves identified on surface ECG that occur during normal sinus node function will be considered for the endpoint. Therefore, P-waves occurring during atrial arrhythmias are not included in the endpoint definition. This criterion was selected so that atrial beats that should not or could not be tracked by the algorithm with a paced or sensed ventricular beat are not included in the endpoint determination. Note that the 300 ms P-V interval required to consider a beat synchronous is identical to what was used for the MARVEL study.

Rationale for 70% AV Synchrony Requirement

There is no recognized consensus on a clinically relevant level of atrioventricular synchrony for subjects with AV block and without AF who require pacing. Importantly, the largest randomized trial (UKPACE) comparing VVI and DDD pacing in patients with normal sinus function and AV block did not identify a difference in pacing modes with respect major clinical outcomes including all-cause mortality, atrial fibrillation, or heart failure.⁸ However, as observed in the MARVEL study, increasing the level of synchrony in this population can increase cardiac stroke volume.⁶

[figure not shown]

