17.5.5 Determination of Subjects and Data for Analysis

All subjects with normal sinus node function and persistent 3rd degree AV block during Holter monitoring with at least 500 evaluable beats during VVI pacing and at least 500 evaluable beats during MARVEL 2 adaptive pacing in which the device is providing VDD pacing¹ will be included in the primary analysis for this objective. For *de novo* subjects, only data collected during the 20-minute resting period at pre-hospital discharge will contribute to the analysis of the primary objective. (Note that ancillary objective number five will compare the atrioventricular synchronous pacing rates observed at pre-hospital discharge and at 1-month post-implant.) However, if a *de novo* subject does not have usable Holter data at pre-hospital discharge, their Holter data approximately 1-month post-implant will be used in the analysis, if available.

¹ Cardiac cycles during MARVEL 2 adaptive mode pacing that occur during an AV conduction test will not be considered evaluable as the pacing mode is set temporarily to VVI40 while the device checks for intrinsic AV conduction.

Loss of communication between the Holter and the implanted Micra device, called telemetry dropout, can lead to loss of the marker indicating a ventricular event was sensed or a ventricular pace was delivered. Therefore, beats with no ventricular sense or pace markers and indication of telemetry dropout in the first 300 ms after a P-wave will be discarded (i.e. they are not evaluable beats).

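### SAP 7.5.3.4 rule 2 leaves part of the AV-conduction-check P-waves in the primary efficacy data, and which ones it leaves is related to the outcome

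*SAP*

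**What the plan says.** The protocol's primary efficacy endpoint (8.2.1.1) requires a ventricular event within 300 ms "for at least 70% of the ECG confirmed P-waves". Footnote 1 to protocol 17.5.5 then narrows what is counted: "Cardiac cycles during MARVEL 2 adaptive mode pacing that occur during an AV conduction test will not be considered evaluable". The reason given there is that the device is temporarily pacing at 40 bpm without atrial tracking. SAP 7.5.3.6 repeats that P-waves during a conduction check are left out of the primary analysis.

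SAP 7.5.3.4 turns this into a data rule. The second class of non-evaluable P-waves is "P-waves that occur during an AV conduction mode switch as these P-waves occur when the pacing mode is set temporarily to VDI40". They are to be found by looking for "a supplemental marker in the preceding P-P interval (column 15 (O) < P-P interval), and the pacing mode in the supplemental marker is VDI40". The same item explains that "the supplemental marker indicates the pacing mode on the next ventricular event", so one has to look back to the preceding marker; that explanation sets no limit on how far back. Any P-wave not caught by the two exclusion rules is evaluable. A subject meets the endpoint if at least 70% of evaluable beats are synchronous.

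On the markers themselves, SAP 7.5.1 says "the Holter records supplemental marker data from the Micra including V-V interval, pacing mode, pacing amplitude" and further settings. SAP 7.5.2, which would define the spreadsheet columns, is redacted.

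**The concern.** The exclusion is stated without exception in two places, but the operational rule carries an extra condition: the VDI40 marker must lie less than one P-P interval before the P-wave. At 40 bpm the ventricular events are 1.5 s apart, which is longer than the P-P interval at any sinus rate above 40 bpm. If markers come with ventricular events, the relevant marker is often out of reach, and the P-wave then falls by default into the evaluable set.

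Whether a P-wave is out of reach depends on how long it comes after the last ventricular event. Whether it is scored synchronous depends on how soon it comes before the next one. At a fixed ventricular rate these are the same quantity, so the exclusion is related to the outcome being measured. Because footnote 1 concerns adaptive pacing, this affects the treatment period and not the VVI control period. Each subject is dichotomised at 70%, so a small shift can change the classification of a subject close to the cut-off.

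**Working it through.** **The plan's own figure.** SAP 7.5.3.5 states more than 90% power for McNemar's test with 35 subjects, 50% discordant pairs, 90% of them favouring MARVEL 2, two-sided 0.05. Recomputed: 94.8% (exact conditional test), 96.9% (asymptotic), 94.0% (continuity-corrected). The claim reproduces, and it does not involve rule 2.

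**Inputs.**
- Ventricular rate in a check: 40 bpm, so V-V = 60/40 = 1.5 s (SAP 7.5.3.4).
- Synchrony window: 0.3 s to the next ventricular event (SAP 7.5.3.4).
- P-P: time since the previous P-wave (SAP 7.5.3.4).
- Assumed: one supplemental marker per ventricular event, with column 15 the time back to the last marker. Inferred from the V-V interval being part of the marker and from its mode referring to the next ventricular event.
- Assumed: P-waves uniformly spread over the V-V cycle.
- Assumed: f, the share of resting P-waves in checks. The visible text gives no value.

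**Timing.** Let x be the time from the last ventricular event to the P-wave. It is flagged if x < P-P, and synchronous if 1.5 − x < 0.3, that is x > 1.2 s. When P-P ≤ 1.2 s (sinus ≥ 50 bpm) the two conditions cannot both hold, so every flagged P-wave is asynchronous.

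**Share kept.** Kept = 1 − P-P/1.5. Synchronous among kept = 0.3/(1.5 − P-P). Share of the asynchronous check P-waves that is kept = (1.2 − P-P)/1.2.

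| Sinus (bpm) | P-P (s) | Check P-waves kept | Synchronous among kept | Asynchronous check P-waves kept |
|---|---|---|---|---|
| 60 | 1.000 | 33% | 60% | 17% |
| 75 | 0.800 | 47% | 43% | 33% |
| 90 | 0.667 | 56% | 36% | 44% |

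**Where the pattern breaks.** In general it needs P-P ≤ V-V − 0.3 s.
- Sinus 45 bpm, pacing at 40: P-P is 1.333 s, so (1.333 − 1.2)/0.3 = 44% of synchronous check P-waves are flagged.
- Sinus 60 with an escape rhythm at 50 bpm (V-V 1.2 s): (1.0 − 0.9)/0.3 = 33% are flagged.
- Sinus 60 with an escape rhythm at 55 bpm (V-V 1.091 s): (1.0 − 0.791)/0.3 = 70% are flagged.

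**Direction.** Kept P-waves raise a 70% subject's score only if 0.3/(1.5 − P-P) > 0.70, that is P-P > 1.07 s, a sinus rate below 56 bpm. Above that rate they lower it.

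**Effect on a subject.** Let s be synchrony with all check P-waves excluded. Under rule 2 the score is [(1 − f)s + 0.2f] / [(1 − f) + kf], where 0.2 = 0.3/1.5 is the synchronous share of check P-waves (all kept) and k = 0.467 at sinus 75.

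| s | f = 1% | f = 2% | f = 5% | f = 10% |
|---|---|---|---|---|
| 71% | 70.9% | 70.7% | 70.3% | 69.6% |
| 72% | 71.9% | 71.7% | 71.3% | 70.6% |

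For example, s = 71% and f = 10% gives (0.639 + 0.020)/(0.900 + 0.0467) = 0.696. The 71% subject drops below 70% once f exceeds 0.01/(0.01 + 0.7 × 0.467 − 0.2) = 7.3%.

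**Short checks.** Phase is then set by the beat at which the check starts. With an assumed entry AV delay of 0.15 s and a three-cycle check, the kept P-waves are all synchronous at sinus 80 (x = 1.35 s, 0.15 s before the next ventricular event). None is synchronous at sinus 90 (x = 1.18, 1.02 and 0.85 s). The direction can therefore differ between subjects.

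**The case against.** The strongest objection is that the premise sits in redacted text. The visible SAP lists what a supplemental marker contains, not how often one is sent, and column 15 is not defined. More frequent markers or a different column definition would shrink or remove the problem. This stands as a condition on the finding. It does not dispose of it, because the visible text ties the marker's mode to the next ventricular event.

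Second, the intent is already clear from protocol 17.5.5 and SAP 7.5.3.6, and the P-P limit may be there to guard against stale markers after telemetry dropout. Both points are fair. But the programmer will follow the operational rule, and a guard against stale markers should be written as one.

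Third, the size rests on an undocumented check frequency. This also stands: at f of 1% or 2%, neither the 71% nor the 72% subject crosses 70%.

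A reader might infer that the rule inflates MARVEL 2 performance, since it flags only asynchronous P-waves. The figures do not support that. Many asynchronous check P-waves are kept too, and against full exclusion the score of a subject near or above 70% mostly falls.

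A reader might also infer that leaving out check beats is itself an error, because the mode switch is one of the features under study (protocol 7.1: "a mode-switch to VVI-40 for patients with paroxysmal AV block who often have intact AV conduction"). Footnote 1 discloses and pre-specifies that exclusion with a reason, so it is a design choice.

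**Conclusion.** Rule 2 as written does not deliver the full exclusion that SAP 7.5.3.6 and protocol 17.5.5 require. On the inferred marker timing and 40 bpm ventricular pacing, it leaves roughly a third to just over a half of check P-waves evaluable at sinus 60 to 90 bpm. The selection is outcome-related in the adaptive period whenever P-P is at most V-V minus 0.3 s. It is not a general bias towards MARVEL 2: above about 56 bpm it mostly lowers scores near or above 70%, and in short checks the direction varies by subject.

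The effect on a subject is a fraction of a percentage point if checks are rare, and about 1.4 points at sinus 75 for s = 71% or 72% if they cover 10% of P-waves. It matters for subjects close to the cut-off. Nothing in the documents shows that the trial's conclusion would change, and the stated power is untouched. It should be corrected because two sections of the SAP disagree on the primary endpoint's input and the correction is small.

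**What to change.** In SAP 7.5.3.4 rule 2, remove the P-P limit and classify each P-wave by the pacing mode in the most recent supplemental marker, which is the mode of the ventricular event that follows. The rule then matches SAP 7.5.3.6 and protocol 17.5.5. State in the same place what column 15 measures and when markers are sent.

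Add a stale-marker rule. Where telemetry dropout lies between that marker and the P-wave, do not carry VDI40 forward unless the mode is confirmed from the next available marker or by Holter review. Without this, a lost return marker would discard valid VDD beats.

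Report the share of resting-period P-waves that fall in checks. A repeat of McNemar's test counting all resting P-waves, including those in checks, is an optional sensitivity analysis.

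The cost is a small change to the spreadsheet logic, some Holter review where dropout coincides with a check, and a rerun on data already collected. The optional analysis would normally show somewhat lower synchrony: at s = 71% and f = 5% it gives 0.95 × 71% + 0.05 × 20% = 68.5%.
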